## 4. Procedures and methods employed for analyzing the data

### Aim 2

*Analysis.* Our analytic approach will focus on use and consequences, cognitions, social networks, and cultural connection outcomes. We will compare opioid education participants to TACUNA+WC participants, with covariates age, gender, and the baseline measure of the outcome of interest. Given the longitudinal design, we may implement more than one analytic method to address this aim. One option is to use a multigroup latent growth model framework using robust maximum likelihood for continuous outcomes or weighted least square mean and variance for categorical outcomes. Alternatively, we may use SAS Proc Mixed will be used for continuous outcomes and SAS Proc Glimmix/NLMixed for categorical outcomes. In addition to examining overall longitudinal trends across the entire study, we will also examine outcomes at each timepoint (3, 6, and 12 month) using multivariable linear regression for normally distributed outcomes and multivariable logistic regression for dichotomous outcomes, controlling for the baseline value of the outcome and participant demographics (age, sex, and sexual and gender diverse identity). The estimated adjusted difference between intervention groups at follow-up (or odds ratio for dichotomous outcomes) and the corresponding 95% confidence interval (CI) will be presented, along with the p-value and Cohen's effect size. Evaluating differences at each timepoint provides estimates of the intervention effect at a given timepoint whereas the longitudinal methods will address patterns of change over the course of the intervention. To enhance interpretability of our results, we will use estimated differences between groups to calculate standardized effect sizes in terms of  $d$  (for continuous variables, using the standard deviation of the opioid education only group as denominator); we will use odds ratio estimates to calculate risk difference and number needed to treat, based on outcome proportions for the opioid education group.

*Power.* The N of 370 was determined in a priori power analyses to be sufficient to detect small to moderate intervention effect sizes for all primary and secondary outcomes. We chose to use the final projected sample size accounting for 20% attrition at the 12-month follow up (n=148 per arm). Within a repeated measures framework, these sample sizes, assuming a correlation between repeated assessments of 0.50, four timepoints, and alpha of .05, we have 80% power to detect a standardized effect size ( $d$ ) of 0.31 between groups and .22 within groups. For mediation models, using bias-corrected bootstrapping, there is 80% power to detect a mediated/indirect effect when  $\delta=0.28$  (i.e., effect of the predictor on the mediator) and  $\beta=0.26$  (i.e., effect of the mediator on the outcome).

### Aim 3

Mediation models will be used to determine whether changes in cultural connectedness and social networks serve as mechanisms for reducing opioid, cannabis, and alcohol use. First we will test multivariate mediation to determine if the total mediation effect is statistically significant to control Type I error rate. If the total mediated effect is significant, we will then examine individual mediators to determine statistical significance. The estimate of the effect of the intervention on the outcome can be divided into the direct effect and the indirect (mediated) effect. The standard errors of the individual indirect effects will be estimated using bias-corrected bootstrapping. For mediation models, using bias-corrected bootstrapping, with these projected sample sizes, there is 80% power to detect a mediated/indirect effect when  $\delta=0.28$  (i.e., effect of the predictor on the mediator) and  $\beta=0.26$  (i.e., effect of the mediator on the outcome). Results will provide information about efficacy for each intervention. Results can improve the design of future studies by providing information such as intra-class correlations within groups, which will allow researchers to estimate sample sizes and effect sizes for power analysis.

## Aim 5

*Costs.* We will account for programmatic costs following the micro-costing approach of prior work. Intervention costs will be obtained from several sources, including program records and primary collection of cost and time use data. Programmatic input costs include labor (including overhead), materials, and other costs of implementing the intervention; for the societal perspective, we will also consider (a) transportation costs to participants; (b) opportunity costs of EAs; and (c) space and utility costs. The analysis will exclude research costs, although we can incorporate these in sensitivity analyses.

*Effectiveness.* We will follow recommendations for economic evaluations of AOD use interventions and consider multiple outcomes from Aim 2 analyses to compare effectiveness at 6 and 12 months after baseline. Our primary effectiveness measures will be abstention from opioid misuse in the past 3 months (either through preventing initiation or discontinuing use); abstention or consumption below the threshold of heavy use for alcohol and cannabis; and a reduction in time spent around peers who misuse opioids. Given our focus on prevention, an effectiveness outcome related to peers will be informative.

*Economic analysis.* We will conduct an intent-to-treat analysis, aligned with the primary analytic plan of Aim 2. We will first perform deterministic analyses (i.e., direct calculations) to sum program costs (and opportunity costs for the societal perspective), yielding incremental net costs as the difference between net costs per participant to (a) those receiving TACUNA+WC and (b) those receiving opioid education. Total costs and costs per participant will be calculated separately by site to assess whether key factors determine cost variability for each intervention. Next, we will perform probabilistic (Monte Carlo) analyses to account for uncertainty and variability in cost parameters. Incorporating Aim 2 findings for each of our primary effectiveness outcomes, we will construct short term incremental cost-effectiveness ratios (ICERs) for each outcome. We will assess model and parameter uncertainty on each outcome's effect sizes, allowing us to consider a range of values from findings related to uncertainty or variability in the relative effectiveness of TACUNA+WC compared to opioid education. We will construct ICER confidence intervals using nonparametric bootstrapping techniques within the multivariable framework, although we may consider other methods.

*Sensitivity analysis.* We will perform sensitivity analyses to test the importance of key model parameters, such as the price of a given resource, on ICER findings. Additionally, we will consider how costs and cost-effectiveness differ under alternative parameter assumptions as well as under different assumptions about attendance.

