## 1. What the study will do

This study responds to Request for Application-DA-19-035, HEAL (Helping End Addiction Long Term) initiative: Preventing OUD in Older Adolescents and Young Adults (ages 16-30) by developing and implementing a culturally centered intervention to address opioid use among urban American Indian/Alaska Native (AI/AN) emerging adults. The primary goal of this behavioral study is to compare AI/AN emerging adults who receive TACUNA (Traditions and Connections for Urban Native Americans) plus a Wellness Circle (WC) to those AI/AN emerging adults who receive an opioid education workshop on outcomes (e.g., opioid misuse and alcohol and other drug use) over a period of 12 months.

- TACUNA will be a virtual motivational interviewing group intervention that incorporates traditional practices and discussion of how to cultivate healthy social networks and cultural worlds. The Wellness Circle will be for emerging adults and people in their social network and will focus on how social networks and cultural connectedness influence healthy behaviors.
- Opioid education (control) will focus on discussion of opioid misuse within the AI/AN urban community and ways to reduce use in a culturally appropriate manner.

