### Phase 2/UH3

Note: Due to the COVID-19 pandemic and restrictions on social gatherings, this study pivoted from in-person group implementation to virtual group implementation. This allowed us to expand participation beyond our original urban sites in California as we were no longer limited by facilitating in-person groups.

In Native American research, it is typical that intervention and control groups receive some degree of an intervention. We will enroll 370 participants at baseline across the United States who we determine represent the broader population of 18-25 year old urban AI/AN emerging adults. In a randomized controlled trial—an unmasked, 2-arm parallel intervention model—participants either will be assigned to TACUNA (n = 185), which comprises three virtual workshops utilizing motivational interviewing, social network visualization, and integrating traditional practices and a Wellness Circle (WC), or to one virtual culturally sensitive opioid education workshop (n = 185). WCs will be culturally focused, and feature Native foods and entertainment (e.g., Native lectures, storytellers, cooking demonstrations, and sage ceremony).

**Aim 2.** We will compare AI/AN EAs who receive TACUNA+WC to AI/AN EAs who receive opioid education. We will compare outcomes at 3, 6, and 12-months to determine (a) whether changes occur in initiation and escalation of opioid use and alcohol and other drug use, such as cannabis, and related consequences; time spent around peers who use opioids and AOD, and perceived prevalence of peer use, (b) whether clinically significant changes occur in physical, social, emotional, and functional well-being, as well as spirituality and cultural connectedness, and (c) if reductions occur, estimate effect sizes.

**Aim 3.** We will explore potential mechanisms of change for decreases in opioid and AOD use outcomes through mediation analyses, including changes in social networks and cultural connectedness.

**Aim 4.** We will develop and test strategies to facilitate sustainability of TACUNA within these communities through key informant interviews upon conclusion of the randomized controlled trial.

**Aim 5.** We will conduct an economic evaluation to quantify programmatic costs and cost-effectiveness of the multi-tiered intervention approach, relative to opioid education.

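### TACUNA is delivered in groups, but the timepoint regressions treat participants as independent; if shared sessions shift whole groups' outcomes, confidence intervals are too narrow and type I error exceeds 5%

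*Combined protocol and SAP*

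**What the plan says.** **Delivery.** Protocol section 1 states: "TACUNA will be a virtual motivational interviewing group intervention that incorporates traditional practices". Under Phase 2/UH3 the protocol reports that "this study pivoted from in-person group implementation to virtual group implementation", and that "participants either will be assigned to TACUNA (n = 185), which comprises three virtual workshops utilizing motivational interviewing"; a Wellness Circle is added. Controls receive "one virtual culturally sensitive opioid education workshop". The documents do not say how many people attend a session, how groups are formed, or whether the control workshop is run in several groups. We read the assignment text as individual randomisation.

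**Analysis.** SAP section 4, Aim 2 Analysis, commits to an arm comparison at each follow-up "using multivariable linear regression for normally distributed outcomes and multivariable logistic regression for dichotomous outcomes". The adjusters listed for these models are the outcome at baseline plus age, sex, and sexual and gender diversity. Neither a workshop-group term nor a cluster-robust variance is named. The longitudinal analysis is left open between a latent growth model and SAS mixed-model procedures, and no workshop-group level is named for either. SAP section 6 confirms that both the timepoint and the longitudinal models compare the arms on the primary outcomes.

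**Power.** SAP section 4, Aim 2 Power, says: "We chose to use the final projected sample size accounting for 20% attrition at the 12-month follow up (n=148 per arm". Its inputs are given as "assuming a correlation between repeated assessments of 0.50, four timepoints, and alpha of .05", leading to 80% power for d = 0.31 between groups. No ICC, group size or design effect is stated. The Aim 3 text expects the results to supply within-group intra-class correlations for planning later studies, but no analysis in this plan is said to use them.

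**The concern.** Participants who share facilitators, discussion and peers over three workshops may end up with outcomes that move together. The sessions deal with peer use, social networks and cultural connection, and these are also measured as outcomes, so a positive ICC is plausible. Individual randomisation does not remove correlation that arises afterwards in the sessions.

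An ordinary regression computes its standard error as if the 148 per arm were independent. If sessions shift whole groups, the true variance of the arm difference is larger than the computed one. The reported interval is then too short and the p-value too small. These are the estimates, intervals and p-values that Aim 2 promises to report at each follow-up.

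**Working it through.** **Inputs from the documents.** 185 per arm; 20% attrition, so 185 × 0.8 = 148 analysed per arm; correlation between repeated assessments 0.50; four timepoints; alpha 0.05 (taken as two-sided, which is not stated); 80% power; d = 0.31.

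**Assumed, because the documents give no value.** Analysed group size m (8, with a range of 5 to 12) and ICC (0.01, 0.02, 0.05).

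**Step 1: the plan's own figure.** With 1.96 + 0.84 = 2.80 and n = 148 per arm:

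- single timepoint: 2.80 × √(2/148) = 0.326
- baseline-adjusted timepoint: 0.326 × √(1 − 0.50²) = 0.282
- mean of four assessments: 0.326 × √((1 + 3 × 0.50)/4) = 0.257

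None of these gives 0.31. Two explanations remain possible. Relative to 0.257, the value 0.31 corresponds to a variance factor of about 1.45, which could hide a clustering allowance. On the other hand, 0.31 between groups and 0.22 within groups both fit a simple unclustered comparison with about 163 per arm: 2.80 × √(2/163) = 0.310 and 2.80/√163 = 0.219. The documents do not settle which is right. The type I results below do not use 0.31.

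**Step 2: effect on the planned test.** DEFF = 1 + (m − 1) × ICC. The variance of the arm difference is inflated by V = (1 + DEFF)/2 if only TACUNA is clustered, and by V = DEFF if both arms are. The interval is too narrow by 1 − 1/√V, and type I error is 2 × (1 − Φ(1.96/√V)). For m = 8:

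| Clustered | ICC | V | Interval too narrow by | Type I error |
|---|---|---|---|---|
| TACUNA only | 0.01 | 1.035 | 1.7% | 5.4% |
| TACUNA only | 0.02 | 1.07 | 3.3% | 5.8% |
| TACUNA only | 0.05 | 1.175 | 7.7% | 7.1% |
| Both arms | 0.01 | 1.07 | 3.3% | 5.8% |
| Both arms | 0.02 | 1.14 | 6.3% | 6.6% |
| Both arms | 0.05 | 1.35 | 13.9% | 9.2% |

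Over m = 5 to 12 and ICC 0.01 to 0.05, type I error runs from 5.2% to 8.3% (TACUNA only) or from 5.5% to 11.5% (both arms).

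**Step 3: simulation of session-induced correlation.** Baseline-adjusted linear regression, 148 per arm, groups of 8, baseline correlation 0.5, ICC on the residual, 20,000 null trials. At ICC 0 / 0.01 / 0.02 / 0.05:

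- ordinary regression: 4.9 / 5.2 / 6.2 / 7.2% (TACUNA only) and 5.0 / 6.1 / 6.5 / 9.1% (both arms)
- cluster-robust with Satterthwaite degrees of freedom: 5.0 / 5.0 / 5.2 / 5.2% and 4.9 / 5.2 / 5.0 / 5.1%

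The logistic models were not simulated.

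**Step 4: correlation from sorting only.** Here individually randomised people are placed in groups by a trait that carries 5% of outcome variance, and the sessions add no group effect. The ordinary test stays at about 5%. The cluster-robust test falls to about 3.6% (TACUNA only) or 2.3% (both arms).

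**Step 5: detectable d for the corrected timepoint regression.** Starting from 0.282, which follows from the stated inputs if 0.50 is the baseline-to-follow-up correlation, 0.282 × √V for m = 8 and ICC 0.01 / 0.02 / 0.05 is 0.29 / 0.29 / 0.31 (TACUNA only) or 0.29 / 0.30 / 0.33 (both arms).

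**The case against.** Four objections deserve weight.

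- **The size is assumed.** This stands. With only TACUNA clustered and ICC 0.01 to 0.02, type I error is 5.4% to 5.8%, which is small. The both-arms figures need control workshops run in several groups, which the documents do not establish.
- **Within-group correlation is not enough by itself.** This stands. A reader might infer that any correlation inside workshop groups inflates type I error. Step 4 shows that correlation due only to how randomised people sort into groups does not, and that the correction is then conservative. The documents do not say how groups form, so the point holds only for effects produced in the sessions.
- **The longitudinal models could carry a group effect.** They could, and the expectation of reporting intra-class correlations suggests that group identifiers may be kept. For those models the gap is under-specification. The timepoint regressions are different: their covariates are listed and no allowance for groups is named. The 0.50 in the power text is a correlation within persons and does not cover people who share a session.
- **The power figure may already include an allowance.** None is stated, but since 0.31 does not reproduce, this cannot be ruled out. A reader might infer that the clustered detectable effect is 0.31 × √V. The documents do not support that, because 0.31 is not a verified unclustered starting value.

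**Conclusion.** The concern holds for session-induced correlation in the timepoint regressions, and as a gap in specification for the longitudinal models. At 8 analysed per group and ICC 0.01 / 0.02 / 0.05, type I error is about 5.4 / 5.8 / 7.1% with only TACUNA clustered and 5.8 / 6.6 / 9.2% with both arms clustered. Both group size and ICC are assumptions. With a zero ICC, or sorting alone, the error stays at 5%.

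On power, the supported statement is narrow: the plan states no ICC or design effect for d = 0.31, and 0.31 does not follow from the stated inputs. A reader might go further and infer that the planned test is seriously underpowered. It is not shown to be. At an effect with 80% nominal power, the uncorrected test at m = 8 and ICC 0.05 still rejects with probability Φ(0.84/√V), which is 78.1% (TACUNA only) or 76.6% (both arms). The fault is over-rejection under the null.

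This should be fixed before analysis. Confidence is medium, because the mechanism is clear but its size cannot be taken from the documents.

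**What to change.** **Data.** Keep an assigned workshop-group ID for every grouped participant. Non-attenders stay in their assigned group. State whether control workshops are run in several groups and how groups are formed.

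**SAP section 4, Aim 2 Analysis.** In the timepoint regressions, use cluster-robust standard errors with a small-sample (Satterthwaite) correction, treating each ungrouped control as a separate cluster. In the longitudinal model, use a workshop-group random effect (TACUNA arm only if controls are not grouped) or cluster-robust variance.

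**SAP section 4, Aim 2 Power.** Show how 0.31 was derived, and restate the detectable d over a stated range of ICC and analysed group size.

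No change to the Aim 3 or Aim 5 bootstraps is required here, since no effect on them was computed. Nor is a multiple-membership model, since the documents describe no reshuffling of groups.

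**Cost.** SAP wording and one variable in the dataset; no additional participants. In the simulation, mean 95% interval width goes from 0.396 to 0.401 at ICC 0, 0.416 at 0.02 and 0.435 at 0.05 (TACUNA only), or to 0.407, 0.434 and 0.470 (both arms). The stated detectable d may become slightly larger. If groups form purely by sorting on a trait related to the outcome, the corrected test is conservative, as shown in step 4 of the working.

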### **5. Who is eligible to take part in it**

Eligibility criteria include: 1) ages 18 to 25; 2) living in an urban area in any state in the United States (not on a rancheria or a reservation); 3) self-identification as AI/AN; 4) no opioid use disorder; and 5) English speaking.

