## 8. What information will be collected

From baseline to 3 months, to 6 months, and to 12 months, we will measure change in:

- a. **Frequency of opioid use.** We will assess frequency of opioid use in the past three months from 1 = never to 6 = over 20 times.
- b. **Frequency of alcohol and cannabis use.** We will assess frequency of opioid use in the past three months from 1 = never to 6 = over 20 times.
- c. **Social Network Composition.** Participants will be asked to name 15 contacts (“alters”) who are at least 18 years of age. Participants will rate each of the 15 people on the same set of questions with categorical response options (about demographics, relationship quality, likelihood to use drugs, etc.). For each participant the selected responses will be summed across all the network alters and divided by 15 to produce network composition percentages of the whole set of alters named by the participant (% of AI/ANs, % who engage in heavy drinking).
- d. **Cultural connection.** Cultural connection will be measured with 29 items that address 3 dimensions: identity, traditions, and spirituality. Respondents answer 11 yes/no questions (e.g., I have a traditional person, Elder, or other person who I talk to), and use a scale from 1= “strongly disagree” to 5= “strongly agree” for 18 items (e.g., I feel a strong connection/attachment towards my Native American community or Tribe). We will also measure this via participation in 26 different types of traditional practices (e.g., going to Pow Wows, beading, traditional dancing). Items were based upon extensive research conducted with AIAN young people, parents, and community partners.
- e. **Social Network Structure.** Participants will rate the relationship strength between each of the 15 named alters. For each alter pair they will rate if the two people know each other and, if yes, have they connected recently. Measures of network structure (i.e. network “connectedness”) will be constructed from the set of evaluations for each participant. For example, network “density” will be constructed for the network overall, which is calculated by summing the number of alter pairs who know each other and dividing by the total number of possible ties among 15 alters (105). Individual alter “centrality” will be calculated by summing the number of connections each individual alter has with other alters in the network.

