## 3. Detailed analyses of data items

*Descriptives.* We will examine descriptive statistics and examine missing data. Frequencies will be evaluated for evidence of sparseness for categorical data and for non-normality (using plots, examination of skewness, kurtosis, etc.) for continuous variables. If sparseness is present for categorical variables, we will collapse as necessary to produce cell sizes sufficient for analysis. Where non-normality is evident, variables may be transformed. Outliers may be recoded or omitted if necessary. Missing data will be dealt with using multiple imputation and/or full information maximum likelihood estimation. All outcomes will be presented using descriptive statistics; continuous variables by the mean and standard deviation (SD), and dichotomous variables by the number and percentage. Descriptive statistics will be provided at both baseline and follow-up.

*Baseline equivalence across experimental groups.* We will evaluate comparability of experimental groups with respect to potential confounders. Categorical methods of analysis (e.g. cross tabulations, chi-square) will be used to compare groups for discrete data (e.g., employment, school status). ANOVA or t-tests will be used to test for homogeneity of groups for continuous data at baseline. If a statistically significant difference is found, the covariates will be included in all subsequent analyses.

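### Visit-specific yes/no outcomes are to be fitted by ordinary logistic regression with at least five terms; if opioid events are rare, the odds ratio may not be estimable, and the SAP's sparseness rule cannot help

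*Combined protocol and SAP*

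**What the plan says.** SAP section 4 (Aim 2, Analysis) plans longitudinal models and, alongside them, a separate model at each follow-up visit. For yes/no outcomes the visit model is "multivariable logistic regression for dichotomous outcomes, controlling for the baseline value of the outcome and participant demographics", the demographics being "age, sex, and sexual and gender diverse identity". Trial arm and the baseline outcome bring the count to five terms. SAP section 3 can raise it: "If a statistically significant difference is found, the covariates will be included in all subsequent analyses".

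The fitted odds ratio is then reused: "we will use odds ratio estimates to calculate risk difference and number needed to treat", based on the control group's outcome proportions.

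On sparse data, SAP section 3 says: "If sparseness is present for categorical variables, we will collapse as necessary to produce cell sizes sufficient for analysis". No other small-sample provision appears.

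The population is described in protocol section 5; the only opioid-related criterion is "no opioid use disorder". Protocol section 2 lists initiation of opioid use among the Aim 2 outcomes. The Aim 5 text in SAP section 4 takes a yes/no opioid measure from Aim 2: "abstention from opioid misuse in the past 3 months (either through preventing initiation or discontinuing use". As collected (protocol section 8), opioid use is a six-level frequency item. The Aim 2 text does not say whether or how it is dichotomised.

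**The concern.** A prevention sample without opioid use disorder, in which use at entry is not required, may report little opioid misuse in a three-month window. Initiation can only occur among those not already using. If either arm has no events, maximum likelihood has no finite arm odds ratio, whatever covariates are in the model. With a few events per arm the estimate exists but is biased and unstable.

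The SAP foresees sparseness, but its remedy is to merge categories, and an outcome that already has two levels cannot be merged further.

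The consequences would spread. The risk difference and number needed to treat are built on the odds ratio. Under multiple imputation, one diverging fit can dominate the pooled result. A failed fit would also force a choice of replacement model after the data are seen, in an unmasked trial.

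**Working it through.** **The plan's own figure.** SAP section 4 (Power) gives detectable standardised effects of 0.31 between and 0.22 within groups: 148 per arm, correlation 0.50, four timepoints, alpha 0.05 (taken as two-sided), 80% power. A linear-trend contrast with equal spacing has variance (1 − 0.5) × 3²/5 = 0.90 over the full span. Between groups: (1.960 + 0.842) × √(2 × 0.90/148) = 0.309. Within: 2.802 × √(0.90/148) = 0.218. Attrition also agrees: 370 × 0.8/2 = 148. The figures reproduce, but they concern standardised effects only. No power or event rate is given for a yes/no outcome.

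**Inputs for the check.** From the documents: 148 per arm and five terms. Assumed: control event rate p0 of 1-10% and a true odds ratio of 0.5.

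**Zero events in an arm.** The treated rate is p1 = 0.5·p0/(1 − p0 + 0.5·p0). With A = (1 − p0)^148 and B = (1 − p1)^148, the chance that at least one arm has no events is A + B − AB. At p0 = 2%: p1 = 0.010/0.990 = 1.01%, A = 0.050, B = 0.223, so 0.050 + 0.223 − 0.011 = 0.262. Expected events are 148 × (p0 + p1).

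| Control rate | Treated rate | Expected events | Events per term | Zero events in an arm (exact) | Arm odds ratio not estimable (simulated) |
|---|---|---|---|---|---|
| 2% | 1.01% | 4.5 | 0.9 | 26% | 25-26% |
| 3% | 1.52% | 6.7 | 1.3 | 11% | 9.5-12% |
| 5% | 2.56% | 11.2 | 2.2 | 2.2% | 1.5-3% |
| 10% | 5.26% | 22.6 | 4.5 | 0.03% | 0-0.1% |

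The last column comes from repeated simulation of the five-term model. The main run used 1,500 trials per setting, a baseline-outcome odds ratio of 10, small demographic effects and baseline prevalence equal to the control rate; another run used a baseline odds ratio of 15. The exact and simulated columns agree.

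**Sensitivity.** With all 370 retained, the arm odds ratio is still not estimable in 18%, 6% and 0.5% of simulated trials at 2%, 3% and 5%. With no treatment effect (odds ratio 1, 148 per arm), the exact chance at 2% is 1 − (1 − 0.050)² = 10%.

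**Bias in the fits that are finite.** The true log odds ratio is −0.693. Main run:

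| Control rate | Ordinary ML, finite fits | Firth, all fits |
|---|---|---|
| 1% | −0.28 | −0.60 |
| 2% | −0.49 | −0.62 |
| 3% | −0.66 | −0.69 |
| 5% | −0.75 | −0.69 |
| 10% | −0.77 | −0.71 |

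At 5% and 10% ordinary ML is too far from zero by 0.057/0.693 = 8% and 0.074/0.693 = 11%; another run gave 6-8%. At 2% and below the finite estimates lie towards 1, because the trials with an infinite estimate have dropped out. Firth is within about 3% at 3-10%, and its standard deviation is about 8% smaller at 5% and 10% (0.68 against 0.74; 0.50 against 0.55).

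**Risk difference.** If only the treated arm has no events, the odds ratio is 0 and the derived difference is simply −p0, with no finite interval for the log odds ratio behind it. If only the control arm has none, an infinite odds ratio is applied to a zero proportion and the result is undefined. Firth does not settle this alone, because its uncorrected predicted risks are pulled towards one half. In 1,000 simulated trials per setting the Firth control risk averaged 2.95% for a true 2%, and 5.83% for a true 5%. The risk difference at 2% was −1.23 points against a true −0.97, that is 1.23/0.97 = 1.27 times too large. Ordinary ML gave −1.02 and the raw difference −1.00.

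**The case against.** The strongest reply is that the event rate is assumed. No document gives one, and at 10% or more infinite estimates practically disappear. That stands, and it limits the point to what may happen.

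It is also fair that the visit-specific models sit beside the longitudinal ones, that Aim 2 never says the six-level opioid item will be dichotomised, and that the explicit yes/no opioid measure appears under the economic evaluation. A reader might infer that the main opioid comparison is set to fail; the documents do not support that.

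A reader might also take divergence of any coefficient (70% of simulated trials at 2%, 38% at 3%) as the failure rate. Those counts include nuisance terms such as baseline use and do not measure failure of the treatment estimate.

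On the remedy, two criticisms hold. Taking the risk difference straight from a Firth fit would make it worse where events are few. And profile penalised-likelihood intervals do not pool by the ordinary multiple-imputation rules, nor does the Firth option combine with full information maximum likelihood, so SAP section 3's missing-data plan has to be matched to it.

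None of this supplies a provision for a sparse two-level outcome; the gap remains.

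**Conclusion.** The concern holds in conditional form. If the control event rate of a yes/no opioid outcome is about 5% or less, ordinary logistic regression at 148 per arm carries a real risk of no finite arm odds ratio: about 25% at 2%, 11% at 3% and 2-3% at 5%. At 5-10% the main effect is a bias of about 6-11% on the log scale, modest beside a standard deviation of 0.55-0.74. At 10% or more the problem is minor.

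These figures rest on an assumed odds ratio of 0.5, the covariate effects stated above, and event rates that the documents do not give.

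Two further inferences go too far. One is that few events always bias the odds ratio away from 1: at 2% or below the finite estimates are biased towards 1. The other is that penalised likelihood removes the problem altogether: it makes the estimates finite and takes out most of the bias, but at 1-2% they stay imprecise and somewhat shrunk (−0.60 and −0.62 against −0.693).

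**What to change.** In SAP section 4 (Aim 2, Analysis):

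1. State how the six-level opioid item becomes a yes/no outcome, and in whom initiation is counted.
2. Fit all visit-specific dichotomous outcomes by Firth penalised logistic regression (an option in SAS), with profile penalised-likelihood confidence intervals for the odds ratio. Applying it to all of them keeps the choice independent of the observed counts.
3. If multiple imputation is used, state how the penalised estimates and intervals are pooled.
4. Do not take risks from the uncorrected fit. Re-estimate the intercept so that the mean predicted risk equals the observed proportion, then derive the risk difference and number needed to treat by standardising over the covariates. Show raw event counts and proportions by arm beside them.

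The cost is a few SAP sentences and some extra programming for the intercept correction and the pooling. At event rates of about 1-2% the odds ratio stays imprecise and somewhat shrunk towards 1, and a risk difference built on it inherits that shrinkage. With plentiful events the results barely change. This does not cover the longitudinal models for categorical outcomes, which face the same sparse-event question and need their own rule.
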